## 2.3 Safety Objective(s)

The safety objectives will be to compare complications from extended use of the WCD with those of the ICD during the study timeframe.

## 2.4 Additional Objective(s)

Echocardiogram core lab determinations will be used to verify local estimates of EF and may be used in secondary analyses of the study data.

## 3 Study Design

## 3.1 General Design

This study is designed as a multi-center prospective observational study of newly diagnosed HF with reduced EF patients to test the hypothesis that additional EF recovery occurs between 90 and 180 days as GDMT is achieved. Although the study doesn't start until day 90, all eligible, consenting patients will be entered into a registry at the start of WCD use. The pre-study registry will allow us to collect early (90 day) outcomes and data in those patients who are likely to be eligible for the study at day 90, or are eligible, but refuse the study at day 90.

#### 3.1.1 Randomization

Because WCD's have been shown to be very effective at treating potentially lethal ventricular tachyarrhythmias and are already FDA-approved and CE marked for use in the study population, randomization will not be done. This observational study will gather information on improvement in EF with medical therapy, WCD use, sudden cardiac arrest event rates, and outcomes within a select group believed to be at high risk for SCD.

[figure not shown]
#### 3.1.2 Blinding

Investigators and treating physicians will not be blinded during the study to any WCD device records that are generally available for physicians to access. This includes ECG and compliance data as recorded by the WCD during patient use.

#### 3.1.3 Expected Duration of Study Participation

The anticipated length of active study participation is 12 months from the start of WCD use.

### 3.1.4 Schematic diagram of study design

#### 3.1.5 Expected Duration of WCD use

WCD use is expected to continue for an additional 90 days post study enrollment (180 days total) for patients with EF  $\leq$  35% and not on GDMT. In the event of an aborted SCA or symptomatic sustained ventricular tachycardia/fibrillation (VT/VF), patients may be implanted with an ICD.

Patients who receive an ICD early (prior to reaching GDMT or not otherwise having an indication for an ICD) versus continuing WCD as described by the protocol will not be considered withdrawn from the study, and will continue to be followed.

Patients who refuse an ICD or WCD continuation as described by the protocol (EF  $\leq$  35%) will not be considered withdrawn from the study, and will continue to be followed.

## 3.2 Primary Study Endpoints

The primary objective of this study is to observe the rate of recovery of ventricular function (EF>35%) between 90 and 180 days in newly diagnosed HF with reduced EF patients being treated with GDMT. The primary endpoints that will be used to support the primary objective are 1) the degree to which GDMT has been achieved, and 2) rates of EF recovery at pre-specified time-points post WCD start.

#### 3.2.1 GDMT

Medications and self-reported adherence to taking those medications as prescribed will be recorded from chart review and patient interview if necessary at day 90, 120, 150, 180, 270, and 360. Medications will also be recorded at the start and end of WCD use.

GDMT will be defined by use of the minimum ACCF/AHA/HFSA/ESC guideline-recommended therapies, such as HF treatments with any renin-angiotensin inhibitor (angiotensin-converting enzyme inhibitor (ACE-I) or angiotensin receptor blocker (ARB) if ACE-I is not tolerated), and reaching target evidence-based doses (or the maximally tolerated levels) of beta-blockers. Mineralocorticoid/aldosterone receptor antagonists (MRAs) are to be included along with ACE-I and beta-blocker treatments, and should be titrated to reach evidence-based doses (or the maximally tolerated levels). Further extension of medications according to current guidelines, including IF-channel inhibitor or angiotensin receptor neprilysin inhibitor will be considered additional HF therapy left to the discretion of the treating physician, but will not be required to define "optimal medical therapy".

#### 3.2.2 LVEF recovery

To support our primary hypothesis that an additional 5% of patients will experience EF improvement between 90-180 days, EF measurement for all patients at 90 (±14), 180 (±14) and 360 (±14)-days after WCD start will be requested and recorded. For this study, EF>35% will be considered as EF improved.

- 3.2.2.1 Echocardiographic assessment of LVEF is most common. Nevertheless, other imaging modalities (MUGA, MRI) may be used to document LVEF at day 0. Although there are likely to be differences in EF assessment among enrolling sites and practices, these differences are not expected to affect the outcome of the trial. At a minimum, we will request a 2-D, M-mode echo at the scheduled time-points.
- 3.2.2.2 Echocardiogram core lab verification. EF is commonly estimated by echocardiogram. Several studies have shown EF measurement to have a wide range of variability that can be observer dependent. Study echocardiograms will be sent to a core lab for a uniform determination of the EF. The core lab determinations will be used to verify local estimates of EF and may be used in secondary analyses of the study data

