## 2 Study Objectives

## 2.1 Primary Objective(s)

The primary objective of this study is to observe the rate of recovery of ventricular function (EF>35%) between 90 and 180 days in newly diagnosed HF with reduced EF patients who were prescribed the WCD while being initiated on their HF medications. This will be measured from EF closest to before hospital discharge, then at 90, 180 and 360-days after WCD start, regardless of continued WCD use, prior EF improvement, or ICD implantation. While approximately one-third of the patients will likely experience EF recovery in the first 90 days, we hypothesize that an additional 5-10% of patients will experience EF improvement between 90 and 180 days as GDMT is achieved. This would be considered clinically significant in terms of the potentially avoided ICD implantations. Outcomes will be tracked and reported for three pre-specified groups based on assessment of SCD risk at 90 days of WCD use:

- 1) Patient improved (EF >35%), SCD risk deemed to be negligible. These patients are expected to end WCD use and not receive an ICD.
- 2) Patient improved EF from start of WCD use (a positive change of at least 5 percentage points in EF), or has a borderline EF of 30-35%, but still has continued SCD risk (EF ≤ 35%). These patients are expected to continue to use the WCD for an additional 3 months.
- 3) Patient not improved from start of WCD use (no change or worsening of EF), EF<30% and has continued high SCD risk. Those on GDMT are expected to be evaluated for an ICD. Those not yet on GDMT may continue the WCD for an additional 90 days.

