## 4 Study Subject

#### 4.1 Inclusion Criteria

The population for this study will be patients who had an ejection fraction (EF)  $\leq$  35% following hospitalization for newly diagnosed HF, and who have already been using a WCD for 90 days. Prior to 90 days, eligible patients will be enrolled into a registry. Registry patients will be enrolled during the first 30 days of WCD use.

All of the following must be true for enrollment into the registry (day 0 – 90 of WCD use):

- 4.1.1 Patients (≥18 years old) who were prescribed the WCD ≤ 10 days post-discharge after hospitalization for a primary reason of newly diagnosed HF with reduced EF (≤30 days since first HF hospitalization), with ischemic or nonischemic cardiomyopathy, and have used the WCD for no more than 30 days.
- 4.1.2 Patients who had an EF  $\leq$  35% during index hospitalization.

All of the following must be true for enrollment into the study (day  $90 \pm 14$ ):

- 4.1.3 Patients (≥18 years old) who were prescribed the WCD ≤ 10 days post-discharge after hospitalization for a primary reason of newly diagnosed HF with reduced EF (≤30 days since first HF hospitalization), with ischemic or nonischemic cardiomyopathy, and either 1) have already used a WCD for 90 ± 14 days or 2) were enrolled in the registry after 01-March-2019 and received an ICD prior to 90 days of WCD use.
- 4.1.4 Patients who had an EF  $\leq$  35% during index hospitalization. Of note, EF at 90  $\pm$  14 days post-hospitalization does not need to be low to be included in the study.

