#### 6.2 Scheduled Visits

- 6.2.1 Clinical and EF reassessment at pre-specified timepoints
  - 6.2.1.1 Upon enrollment into the pre-study registry, baseline clinical data will be recorded from chart review and patient interview if necessary.

6.2.1.2 After enrollment into the study, additional clinical data will be recorded from chart review and patient interview if necessary at 90, 120, 150, 180, 270 and 360 days post WCD start. This data will include medications, ER visits, HF hospitalizations, survival, ICD placement, and last known clinical status.

A subset of sites will also collect quality of life (QOL), patient reported data at baseline (registry enrollment), 90 (±14), and 180 (±14) days of WCD use. QOL data from 350 enrolled patients (from US and Europe) will be collected using the Kansas City Cardiomyopathy Questionnaire (KCCQ-12).

- 6.2.1.3 EF measurement at 90 ( $\pm$ 14), 180 ( $\pm$ 14) and 360 ( $\pm$ 14)-days post WCD start will be requested and recorded. Any additional EF measurements taken at the end of WCD use will be collected as well, if not at one of these already pre-specified timepoints (see 6.3.1.2).
  - 6.2.1.3.1 Echocardiographic assessment of LVEF is most common. Nevertheless, other imaging modalities (MUGA, MRI) may be used to document LVEF at day 0. Although there are likely to be differences in EF assessment among enrolling sites and practices, these differences are not expected to affect the outcome of the trial. At a minimum, we will request a 2-D echo at the scheduled time-points.

The following scheduled visit is for all registry patients:

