## 8.3 Endpoint Assessment

## 8.3.1 Primary Endpoint – LVEF recovery and GDMT

Descriptive or summary statistics of serial EF measurements will be used to analyze the rate of recovery of ventricular dysfunction following discharge. For example, the means of EF at 180 days will be compared to the means of EF at baseline and 90 days. The percentage of patients reaching the goal of EF>35% will be compared at 90 days and 180 days. Also, the time taken to reach EF>35% will be calculated for those who improve, and compared between groups (based on baseline characteristics). Individual patient EF measurements over time will be compared to determine whether common patterns arise in certain groups of patients (fast recovery/slow recovery, plateaued recovery/peaked recovery followed by decline). The influence of baseline characteristics on the potential for recovery will be evaluated.

Descriptive statistics will be used to assess the degree GDMT was reached at 90 and 180 days, and how GDMT relates to EF recovery. We will also assess how adherence to the GDMT regimen affects EF recovery and overall clinical improvement.

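### Day-0 EF may come from MUGA or MRI while follow-up EF is requested by echo, so baseline-referenced EF results can mix a method difference with recovery; the 90-to-180-day comparison is not directly affected

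*Combined protocol and SAP*

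**What the plan says.** Section 3.2.2.1 allows that "other imaging modalities (MUGA, MRI) may be used to document LVEF at day 0" and then adds: "At a minimum, we will request a 2-D, M-mode echo at the scheduled time-points". Section 6.2.1.3.1 repeats the allowance. Both sections acknowledge that EF assessment will differ among sites and practices, and conclude that "these differences are not expected to affect the outcome of the trial".

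On the baseline reading, Section 2.1 says: "This will be measured from EF closest to before hospital discharge". It names no modality. Entry under Section 4.1 requires an EF of no more than "35% during index hospitalization", also without naming a modality.

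Four planned outputs look back to that reading:

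- Section 8.3.1 states that "the means of EF at 180 days will be compared to the means of EF at baseline and 90 days".
- The same section examines individual EF patterns over time (fast, slow, plateaued, or peaked then declining).
- Section 3.2 makes EF recovery rates at the pre-specified time-points a primary endpoint. For day 90 this means moving from an entry EF of 35% or less to above 35%.
- Section 2.1 defines group 2 partly by "a positive change of at least 5 percentage points in EF" since the start of WCD use.

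On central reading, Section 3.2.2.2 says: "Study echocardiograms will be sent to a core lab for a uniform determination of the EF". Those readings verify local values and may be used in secondary analyses.

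**The concern.** A difference between sites largely cancels in a within-patient change if each patient keeps one method throughout. A change of method within a patient does not cancel: the offset between methods becomes part of that patient's apparent recovery. The reassurance in Sections 3.2.2.1 and 6.2.1.3.1 is about differences among sites and practices, comes with no figure or analysis, and does not address this case. The core lab does not remove the problem either, because it reads echocardiograms only and an MRI or MUGA baseline gets no uniform reading.

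At stake are the size of the reported EF gain from baseline, the description of early recovery, and the group under which some patients' outcomes are reported.

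**Working it through.** The plan states no figure for this issue, so there is nothing to reproduce. The check is which outputs are exposed, and then how large the effect could be under stated assumptions.

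**Step 1. Which comparisons cross methods?**

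| Output | First reading | Second reading | Exposed? |
|---|---|---|---|
| EF >35%, day 90 against day 180 (8.3.1; hypothesis in 3.2.2) | Echo, as requested | Echo, as requested | Not directly |
| Mean EF, day 180 against baseline (8.3.1) | Any modality | Echo | Yes |
| Individual trajectories starting at day 0 (8.3.1) | Any modality | Echo | Yes |
| Recovery by day 90 from entry EF ≤35% | Any modality | Echo | Yes |
| Group 2 against group 3 (2.1) | Any modality | Echo | Only if day-90 EF <30% |

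The last row is limited because Section 2.1 puts a day-90 EF above 35% in group 1, and one of 30-35% in group 2 whatever the change. The 5-point rule decides only below 30%. Even there, a gain of 1-4 points fits neither group 2 nor group 3 as worded.

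**Step 2. Assumptions.** The documents say only that echo is the most common method. I assume:

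- share of patients with a non-echo baseline: 5-30%;
- offset (echo minus baseline method): 3-5 EF points, in either direction;
- SD of the observed difference between two readings: 7 points, with 4-8 as a range.

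**Step 3. Shift in mean change from baseline** = share × offset.

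- 5%: 0.05 × 3 = 0.15 to 0.05 × 5 = 0.25 points
- 10%: 0.10 × 3 = 0.3 to 0.10 × 5 = 0.5 points
- 30%: 0.30 × 3 = 0.9 to 0.30 × 5 = 1.5 points

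The sign follows the offset.

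**Step 4. Chance that a patient with no true change, a non-echo baseline and day-90 EF <30% meets the 5-point rule** = 1 − Φ((5 − offset)/SD).

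| Offset | SD 7 | SD 4 to 8 |
|---|---|---|
| 0 | 1 − Φ(0.714) = 24% | 11-27% |
| +3 | 1 − Φ(0.286) = 39% | 31-40% |
| +5 | 1 − Φ(0) = 50% | 50% |
| −3 | 1 − Φ(1.143) = 13% | 2-16% |
| −5 | 1 − Φ(1.429) = 8% | 1-11% |

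A true gain can be hidden in the same way. For a true change of +10 points, the chance of meeting the rule is 73-89% with no offset (SD 8 to 4) and 50% with an offset of −5.

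**Step 5. Recovery by day 90.** With an offset of +3, an unchanged patient whose entry MRI gave 33% would read 33 + 3 = 36% on a noise-free echo at day 90 and count as recovered.

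**The case against.** The strongest reply is that the study's question is untouched. The hypothesis and the sample size in Section 8.1.1 concern improvement between days 90 and 180; MUGA and MRI are mentioned only for day 0; and echo is requested at both later visits. This stands. A reader might infer that the main hypothesis is biased by modality, and the documents do not support that.

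Second, the exposed mean comparison is introduced in Section 8.3.1 as an example of descriptive analysis, and echo is described as the most common method. At a 5% non-echo share the mean shift is at most 0.25 points. This also stands, and it limits the importance of the point.

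Third, ordinary noise matters too. With the same method at both times and SD 7, 24% of unchanged patients would still meet the 5-point rule, and pairing methods leaves that noise in place. True, but an offset adds a systematic error that further patients do not average away.

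Fourth, echo data are already collected at registry entry (Section 6.2.2.3 and Table 1), so few patients may lack an early echo. That makes the repair easy but does not make it: no section says that this echo replaces an MRI or MUGA value as baseline. Because Section 2.1 takes the reading closest to before discharge, a later MRI could displace an earlier echo.

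Two further inferences are tempting and fail. One is that every non-echo baseline shifts results in the same direction. The documents give neither sign nor size, and MUGA and MRI offsets may differ in sign and partly cancel. The other is to multiply share by change in probability, for example 0.30 × (0.500 − 0.238) = 7.9%, and call that the proportion of all unchanged patients relabelled. It would have to be multiplied again by the share of those patients with day-90 EF below 30%, which is unknown.

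**Conclusion.** The point holds for baseline-referenced results only and is a cheap improvement rather than a threat to the study's main conclusion. As written, the plan lets any method offset enter EF change from day 0, trajectories, recovery by day 90 and, below a day-90 EF of 30%, the reported split between groups 2 and 3. The effect can be large for an affected patient. On the overall mean it is small unless non-echo baselines are common. All magnitudes rest on the assumed share, offset and SD; what the documents themselves establish is the mixing of methods and the absence of any rule to handle it.

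**What to change.** For analysis and reporting only, altering no clinical decision:

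1. Record the modality and date of the day-0 EF. Section 12.1 lists echo reports but names no modality item; the case report form is a separate document that may already hold it.
2. State which reading is the analysis baseline. Where a day-0 echo exists, use it. Define how close to day 0 it must be, since the registry visit runs to day 30.
3. Report change from baseline, trajectories, recovery by day 90 and the group split on echo-to-echo pairs, beside the all-modality result, and give the number of non-echo baselines.
4. Keep patients without a day-0 echo in their all-modality group, flagged, so that nobody is left without a reported group.
5. In Sections 3.2.2.1 and 6.2.1.3.1, limit the statement that assessment differences should not affect the outcome to the 90-to-180-day comparison.

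The cost is wording in the statistical plan, possibly one data item, and fewer patients in the echo-to-echo change analysis. How many fewer cannot be said from the documents.

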## 5.2 Study Size

Up to 1400 subjects will be enrolled into the pre-study registry, and up to 600 may be enrolled in the study portion. Thirty to eighty sites will enroll patients into the study. Sites will initially be located in the United States and Germany, but may be expanded to other European countries. Individual sites will only be allowed to enroll up to 140 patients (or 10% of the total population).

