#### 8.1.1 Statistical design used for sample size calculation

This dataset will be used evaluate among all patients, if more than 5% of them will experience EF improvement between 90 and 180 days ( $n_5/n > 5\%$ ).

To calculate the number of samples (n), we first calculated  $n_4$ , then calculated n based on the following formula:

$$n = \frac{n_4}{P_{followup2}} * \frac{1}{p_{wcd}} * \frac{1}{P_{followup1}}$$

where  $p_{wcd}$  is the percentage of patients who will wear WCD beyond 90 days ( $n_1/(n_1+n_2+n_3)$ ,  $p_{followup1}$  and  $p_{followup2}$  are the percentage of patients with proper follow up from 0 to 90 days and from 90 days to 180 days respectively, both of the them equals to 0.85 (1-0.15=0.85).

To calculate sample size for  $n_4$ , we performed superiority test. The statistical hypothesis to be tested is:

[figure not shown]
$$H0: P \le P_0 + \delta \text{ vs } H1: P > P_0 + \delta$$

The sample size of superiority test is calculated as the following formula:

$$n_4 = p(1-p) \left( \frac{Z_{1-\alpha} + Z_{1-\beta}}{p - p_0 - \delta} \right)^2$$

where p is the actual proportion of patients who will have EF improvement ( $n_5/n_4$ ).  $p_0$  is the baseline proportion, and specified as 0.001 (close to 0).  $\delta$  is the test margin, since the hypothesis is that more than 5% of them will experience EF improvement between 90 and 180 days ( $n_5/n > 5\%$ ),  $\delta$  depends on  $p_{wcd}$  as  $\delta = 0.05/P_{wcd}$ . We also specify  $\alpha$  as 0.05,  $\beta$  as 0.1

As shown in figure above, sample size (n) depends both on p, the actual proportion of patients who will have EF improvement (p=n5/n4) and  $p_{wcd}$ , the percentage of patients who will wear WCD beyond 90 days ( $p_{wcd} = n_1/(n_1+n_2+n_3)$ ).In this study, we specify  $\alpha$  as 0.05,  $\beta$  as 0.1. We predict that about 1/3 patients will have continued WCD wear from 90 to 180 days; and actual proportion of WCD patients at 90 days to have further EF improvement is 23%. In this case, we plan to prescribe WCD to 868 patients (initial registry sample size), in order to have approximately 738 patients eligible for the study at day 90. If mid-study analysis shows continued WCD use to be far out of 1/3, then sample size will be re-adjusted as necessary.

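### Site differences in EF reading are expected but dismissed without support, and neither the primary test nor the analysis plan allows for correlation within site

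*Combined protocol and SAP*

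**What the plan says.** - **EF reading.** Section 3.2.2.1 accepts that sites and practices will probably assess EF differently, then says "these differences are not expected to affect the outcome of the trial". Section 6.2.1.3.1 repeats this. Neither gives a reason.
- **Core lab.** Section 3.2.2.2 notes that EF measurement varies widely with the observer, and provides that "Study echocardiograms will be sent to a core lab for a uniform determination of the EF". Those values are to verify the local ones and "may be used in secondary analyses of the study data". Section 2.4 says the same. No section makes core-lab EF the primary measurement.
- **Primary test.** The one formal test is in section 8.1.1: "we performed superiority test". It is a one-sample, one-sided test at 0.05 with variance p(1-p). Section 8.3.1 describes the primary analysis as descriptive or summary statistics. Section 8.4 refers to the rest of the protocol and section 8.5 is marked not applicable.
- **Sites and sizes.** Section 5.2: "Thirty to eighty sites will enroll patients into the study"; "Up to 1400 subjects will be enrolled into the pre-study registry, and up to 600 may be enrolled in the study portion"; "Individual sites will only be allowed to enroll up to 140 patients (or 10% of the total population".
- **Tested group.** Section 8.1.1 keeps a goal of 200-250 patients in the extended-wear group.

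**The concern.** The endpoint is a cut at EF 35%. A site that habitually reads a little high or low near that value moves several of its patients across the line together. Medication adjustment and decisions on continuing the device or implanting an ICD are also made locally, so some correlation within site is plausible even with perfect EF reading. A binomial variance treats each patient as independent and ignores this.

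Precision matters because the expected result is near the margin. Section 2.1 hypothesises 5-10% late recovery, and the planning values imply 0.23 × 1/3 = 7.7% of all patients, against a margin of 5%. An understated standard error could turn an inconclusive result into a claimed one.

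The limit on any one site's contribution is also unclear, because it does not say whether it applies to the registry or to the study.

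**Working it through.** **1. Does the planned sample size allow for site?**

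Inputs from section 8.1.1: p = 0.23, p0 = 0.001, p_wcd = 1/3, so δ = 0.05/(1/3) = 0.15; α = 0.05 one-sided; β = 0.10; follow-up 0.85 in each period.

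- Printed formula: n4 = 0.23 × 0.77 × ((1.645 + 1.282)/(0.23 − 0.001 − 0.15))² = 243. Then n = 243 × 3/(0.85 × 0.85) = 1009, not the stated 868.
- With the null variance in the α term, p0 = 0 and p_wcd = 0.33: n4 = 207 and n = 868. Also 868 × 0.85 = 738, as stated.

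So 868 comes from a standard variant rather than from the printed formula, and the two should be reconciled. For the present point, no version contains a site term or design effect. The inputs to the later recalculation (600 and 1400) are not shown.

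**2. Effect of correlation within site**

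Inputs: 200-250 extended wearers (8.1.1) and 30-80 sites (5.2). Mean site size m runs from 200/80 = 2.5 to 250/30 = 8.3. The documents give neither an intra-site correlation (ICC) nor a coefficient of variation (CV) of site size. I assume ICC 0.02 and 0.05, and CV 0 (equal sites) and 1 (uneven sites).

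- Design effect: DE = 1 + (m(1 + CV²) − 1) × ICC
- Standard error factor: √DE
- True one-sided error of a nominal 5% test: 1 − Φ(1.645/√DE)

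| ICC | CV | DE (m = 2.5; 8.3) | SE factor | True one-sided error |
|---|---|---|---|---|
| 0.02 | 0 | 1.03; 1.15 | 1.01; 1.07 | 5.3%; 6.2% |
| 0.05 | 0 | 1.08; 1.37 | 1.04; 1.17 | 5.6%; 8.0% |
| 0.02 | 1 | 1.08; 1.31 | 1.04; 1.15 | 5.7%; 7.6% |
| 0.05 | 1 | 1.20; 1.78 | 1.10; 1.34 | 6.7%; 10.9% |

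Example (ICC 0.05, CV 1, m = 8.3): DE = 1 + (16.67 − 1) × 0.05 = 1.78; √1.78 = 1.34; 1.645/1.34 = 1.23; error 10.9%.

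If some sites contribute no extended wearers, m rises among the rest and the effect grows.

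**3. The site limit**

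- 140/1400 = 10.0%, so 140 matches the registry total.
- 140/600 = 23.3%, reached only if every registry patient at a full site enters the study.
- At the overall conversion of 600/1400 = 43%, that site supplies 140 × 600/1400 = 60 study patients, and 60/600 = 10%.

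No separate limit is written for the study, or for the 200-250 extended wearers to whom the test applies.

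**The case against.** **The core lab is already there.** It gives a uniform reading and speaks directly to site reading habits, so a reader who infers that the plan leaves EF differences with no safeguard goes too far. What remains is that core-lab EF has no pre-specified role in the primary result, and that it cannot remove differences in titration or case mix. Conversely, a clustered variance widens the interval but does not correct reader bias. The two remedies do different jobs.

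**No interval is specified.** A reader might conclude that the study's error bars are too narrow. The documents do not support that as fact: the binomial variance stands in the sample-size section, and section 8.3.1 gives no variance or interval method. The statement must be conditional on that variance being used and on positive correlation within site.

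**The size rests on assumptions.** With 80 equal sites and ICC 0.05 the standard error factor is only 1.04. This objection stands, although equal sites are the optimistic case: section 5.1 seeks out sites that prescribe the device heavily. That EF reading, titration and device decisions are driven by site is plausible but not shown. Sections 2.1 and 3.1.5 tie expected device continuation to EF and GDMT status, and section 7 places prescribing with the physician.

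**23% is a ceiling.** It is tempting to read section 5.2 as letting one site supply nearly a quarter of the study. That would need complete conversion at a site already at its limit, and the total in the 10% clause can also be read as the study total.

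**Conclusion.** The concern holds in conditional form. The protocol names a likely source of between-site variation, dismisses it without evidence, and provides no analysis that would show whether the dismissal is right. The only formal test assumes independent patients. If that variance is used and outcomes are positively correlated within site, the one-sided error is about 5.3-8.0% with equal sites and 5.7-10.9% with uneven sites (CV 1), for ICC 0.02-0.05. The effect therefore runs from negligible to moderate, and the documents do not allow it to be placed more exactly.

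The site limit is a matter of unclear wording: 140 is 10% of the registry, at most 23% of the study, and about 10% of the study at average conversion.

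**What to change.** 1. In section 8.3.1, specify the interval and test for the 90-180 day recovery proportion with site as the cluster (cluster-robust variance or GEE, with a small-sample correction).
2. Add a leave-one-site-out check for the largest sites.
3. Pre-specify a sensitivity analysis of the same proportion using core-lab EF. Echocardiograms are requested at both day 90 and day 180, and study echocardiograms already go to the core lab.
4. Delete the statement that site differences will not affect the outcome, in both 3.2.2.1 and 6.2.1.3.1.
5. In section 5.2, state whether the 10% limit refers to the registry, the study or both.

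**Cost.** Items 1-4 need text changes and a little more analysis, with no new data. The interval widens by the SE factors in the table: 1-17% with equal sites, 4-34% with uneven sites. Item 5 as worded is a clarification. Imposing a hard limit of 60 study patients per site would be a change to the enrolment rules and a separate decision, since it could stop recruitment early at a large site.
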